2.3.2 Single-Arm Cohort

2.3.2.1 Single-Arm Cohort – Primary Endpoint

The primary endpoint of the Single-arm Cohort is survival at 12 months with a quality of life improvement (assessed using KCCQ overall score) of at least 10 points compared to baseline. This endpoint will be assessed as a proportion of subjects meeting the definition of the endpoint.

The null and alternative hypotheses are stated as:

H₀: $P(12M) \leq 30\%$ vs.

H₁: $P(12M) > 30\%$

where $P(12M)$ represents the proportion of subject survival at 12 months with a quality of life improvement (assessed using KCCQ overall score) of at least 10 points compared to baseline. [REDACTED]

[REDACTED]
[REDACTED]
[REDACTED]
[REDACTED] The primary analysis will be performed on the Attempted Procedure population and the null hypothesis will be rejected at a one-sided 2.5% level of significance.

The performance goal was set based on the following clinical assumptions:

- [REDACTED]
[REDACTED]

Statistical Analysis Plan

[REDACTED]

2.3.2.2 Single-Arm Cohort – Secondary Endpoint

2.3.2.2.1 TR Reduction by at least 1 Grade at 30-Day Follow-up

The TR reduction by at least 1 grade at 30-day post procedure is the secondary measure of effectiveness for TriClip™ in the Single-Arm Cohort. The analysis of this secondary endpoint is a one-group test against an objective performance goal of 50%.

The null and alternative hypotheses are stated as:

$$H_0: P_{30D,TR} \leq 50\%$$

$$H_1: P_{30D,TR} > 50\%$$

where $P_{30D,TR}$ represents the proportion of subjects in the Single-Arm Cohort with TR reduction by at least 1 grade at 30-day follow-up. [REDACTED]

[REDACTED]

An exact test for a binomial proportion will be used to test the null hypothesis at a one-sided 2.5% level of significance.

2.3.2.2.2 Freedom from Major Adverse Events (MAE) at 30 Days Post Procedure

The freedom from MAE occurring after procedure attempt (femoral vein puncture) at 30 days is the secondary measure of safety for TriClip™ in the Single-Arm Cohort. The analysis of this secondary endpoint is a one-group test against an objective performance goal of 80%.

The null and alternative hypotheses are stated as:

$$H_0: P_{30D} \leq 80\%$$

$$H_1: P_{30D} > 80\%$$

where P_{30D} is the probability of freedom from any MAE at 30-day post procedure. A [REDACTED]

[REDACTED]

Statistical Analysis Plan

[REDACTED]

The null hypothesis will be rejected at a one-sided 2.5% level of significance.

2.3.2.2.3 Change in 6MWT (Six Minute Walk Test) Distance at 12 Months over Baseline

Improvement in the 6MWT distance at 12 months from baseline is an important secondary effectiveness endpoint.

The null and alternative hypotheses are stated as:

$$H_0: \mu_{\Delta 6MWD} \leq 0 \text{ vs.}$$

$$H_1: \mu_{\Delta 6MWD} > 0$$

where $\mu_{\Delta 6MWD}$ represents the mean change in 6MWT distance at 12 months from baseline.

The analysis will be performed in subjects with paired 6MWT data at baseline and 12 months. [REDACTED]

[REDACTED] Paired t test will be used to compare the mean change to 0 and the null hypothesis will be rejected at a one-sided 2.5% level of significance.

2.3.2.2.4 Recurrent HF Hospitalizations at 12 Months

The null and alternative hypotheses are stated as:

$$H_0: \lambda_{12M}(\text{PRE}) \leq \lambda_{12M}(\text{POST}) \text{ vs.}$$

$$H_1: \lambda_{12M}(\text{PRE}) > \lambda_{12M}(\text{POST})$$

where $\lambda_{12M}(\text{PRE})$ and $\lambda_{12M}(\text{POST})$ represent the annualized event rates for recurrent HF hospitalizations within 12 months prior to (PRE) and on or after (POST) study enrollment.

[REDACTED]

[REDACTED]

The null hypothesis will be rejected at a one-sided 2.5% level of significance.

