**TRILUMINATE Pivotal CIP**  
(Version F)

	
 
○ New Onset Renal Failure,
 
○ Endocarditis Requiring Surgery, and
 
○ Non-Elective Cardiovascular Surgery for TriClip™ device-related AE post-index procedure.
 
 
 
● Change in Kansas City Cardiomyopathy Questionnaire (KCCQ) at 12 months
 
● Change in Six Minute Walk Test (6MWT) at 12 months
 
 
In addition, the following secondary endpoints will be assessed after all randomized subjects complete 24 months follow-up:
 
 
● Recurrent HF hospitalizations at 24 months
 
● Freedom from all-cause mortality, tricuspid valve surgery, and tricuspid valve intervention at 24 months
 
 
Single-arm Cohort
 
 
● TR Reduction by at least one grade at 30-day post procedure as compared to baseline.
 
● Freedom from major adverse events (MAE) occurring after procedure attempt (femoral vein puncture) at 30 days. Components of MAE consist of the following: 
 
○ Cardiovascular Mortality,
 
○ New Onset Renal Failure,
 
○ Endocarditis Requiring Surgery, and
 
○ Non-Elective Cardiovascular Surgery for TriClip™ device-related AE post-index procedure.
 
 
 
● Change in 6MWT at 12 months, as compared to baseline
 
● Recurrent HF hospitalizations at 12 months compared to the 12 months prior to enrollment
 
● Freedom from all-cause mortality and tricuspid valve surgery at 12 months
 

Descriptive Endpoints	
The following descriptive endpoints will be assessed and reported:
 
 
● Technical Success
 
● Device Success
 
● Procedural Success
 
● Incidence of peripheral edema requiring hospitalization at 12 months, and annually through 24, 36, 48, and 60 months
 
● Incidence of ascites at 12 months, and annually through 24, 36, 48, and 60 months
 

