## **6.4 Subject Enrollment**

A patient is considered enrolled in the clinical investigation from the moment the patient provides written informed consent and has been confirmed to meet all inclusion criteria and none of the exclusion criteria. .

Subjects will be assigned a subject ID upon informed consent and entry into the database. Such subjects are registered in the trial.

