### 7.3 Baseline

#### 7.3.1 Baseline Clinical Assessments

Baseline visit must be performed within 14-days after eligibility has been confirmed by the EC.

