### **7.6 Index Procedure (Roll-In, Device Group and Single-arm Cohort)**

The index procedure must be performed within 0 to 14 days after randomization (baseline visit for Single- cohort and Roll-in cohort). If complications arise during the procedure, it may be necessary to convert to an open surgical procedure. Emergency surgical back-up should be available as per the institution's standard procedures.

The Sponsor will be available to provide technical support to answer questions regarding the function and operation of the TriClip™ System. Refer to the IFU for specific instruction on the use TriClip™ device, including handling requirements, preparation for use and precautions.

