## TRILUMINATE Pivotal CIP (Version F)

TriClip™ procedure. **This echocardiogram will not be submitted to the ECL.** If an intracardiac mass, thrombus or vegetation or other change in echocardiographic eligibility is identified in the TEE performed immediately preceding the procedure, the procedure should be postponed until the change can be carefully evaluated by site and sponsor. If a thrombus is identified, the subject should be pharmacologically treated to resolve the thrombus and, if successful, the subject should be reassessed as soon as possible to undergo the TriClip™ procedure. Such subjects will be considered enrolled even if they do not undergo the TriClip™ procedure.

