### **7.10.2 Follow-up for All Subjects**

Required clinical follow-up will be performed at the following intervals (based on treatment visit) for all subjects with TriClip™ procedure attempt, regardless of whether a TriClip™ was successfully implanted:

- Discharge post-TriClip™ procedure
- 30 days (-3/+14 days) follow-up visit (this visit must be conducted even if subject is in hospital)
- 6 months (180 days ± 28 days) follow up visit
- 1 year (365 days ± 28 days) follow up visit
- 18 months (545 days ± 28 days) follow up visit
- 2 years (730 days ± 28 days) follow up visit
- 3 years (1095 days ± 28 days) follow up visit
- 4 years (1460 days ± 28 days) follow up visit
- 5 years (1825 days ± 28 days) follow up visit

Follow-up visits will be calculated from the date of the Index Procedure (for subjects receiving the device) and the Treatment visit for subjects in the Control group. Follow-up assessments can be performed at any point in the window, and should be conducted, whenever possible, by the same individual who performed the baseline tests. The subject should be followed at the investigational site where the subject was enrolled and may be followed at another investigational site only with prior agreement from that site’s Investigator and from the Sponsor.

At the 30-day follow-up visit, the echocardiographer shall examine the integrity of the TriClip™. Subjects must continue to take baseline medications without change during follow-up, unless clinically (medically) necessary. If there are any cardiovascular medication changes (including dosage changes), these changes should be documented on the electronic case report form. In general, neurohormonal antagonists should not be changed. Subjects implanted with the

Study Document No: ABT-CIP-10249

Study Name: TRILUMINATE Pivotal

**CONFIDENTIAL:** May not be reproduced outside of Abbott without written permission from Document Control. This is a quality record which will be retained per the local retention policy.

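### The Single-arm recurrent HF-hospitalization test starts its POST window at enrollment, so 0 to 28 scheduled days before the procedure count as post-treatment time

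*SAP*

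**What the plan says.** SAP 2.3.2.2.4 defines the two annualized rates by a single date, counting events "within 12 months prior to (PRE) and on or after (POST) study enrollment". The Protocol Summary uses the same anchor for the comparator: "Recurrent HF hospitalizations at 12 months compared to the 12 months prior to enrollment". Protocol 5.2.2 and SAP 1.4.2.2 mention only the prior 12 months and name no anchor.

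Enrollment comes before treatment. Under Protocol 6.4 it requires written consent and that the patient "has been confirmed to meet all inclusion criteria and none of the exclusion criteria". It does not depend on a device being placed. Protocol 7.6.2.4, on procedures postponed for an echo finding, states: "Such subjects will be considered enrolled even if they do not undergo the TriClip™ procedure".

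Two scheduling windows then follow. Protocol 7.3.1: "Baseline visit must be performed within 14-days after eligibility has been confirmed by the EC". Protocol 7.6: "The index procedure must be performed within 0 to 14 days after randomization (baseline visit for Single- cohort and Roll-in cohort".

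Other clocks in the plan start at the procedure. Protocol 7.10.2 says "Follow-up visits will be calculated from the date of the Index Procedure (for subjects receiving the device". The Single-arm MAE endpoint in SAP 2.3.2.2.2 counts events after femoral vein puncture. The sentence in SAP 2.1.1 that starts analysis follow-up at the Treatment visit sits under the Randomized Cohort heading, and no visible sentence gives the Single-arm cohort the same start.

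Hospitalizations in the interval are recorded. Protocol 8.3.1 starts safety reporting at enrollment, and Table 1 in Protocol 7.15 has hospitalization entries at baseline and procedure.

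**The concern.** The test asks whether HF hospitalizations fall after treatment. If POST opens at enrollment, an admission between eligibility confirmation and the procedure counts as a post-treatment event, although no device is in place. The person-time of that interval also enters the POST denominator. The POST rate becomes a mixture of untreated and treated time, and the share of each depends on how long each subject waited.

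At stake is a labeling-claim test (SAP 2.11.2) for which SAP 2.4.2.2.4 states about 83% power with about 100 subjects. SAP 2.4.2.2 states that the Single-arm secondary endpoints have at least 80% power at that size. The result should not depend on scheduling delay. This point is separate from the lack of a concurrent control in a before-and-after comparison.

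**Working it through.** **Length of the gap.** Protocol 7.3.1 allows 0 to 14 days from Eligibility Committee confirmation to baseline. Protocol 7.6 allows 0 to 14 days from baseline to procedure. The scheduled range is therefore 0 to 14 + 14 = 28 days. As a share of a 365-day POST window, 14/365 = 3.8% and 28/365 = 7.7%. If POST instead runs from enrollment to 12 months after the procedure, the longest scheduled gap is 28/393 = 7.1%.

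**The plan's own figure.** The 83% cannot be reproduced, because the rates and other inputs in SAP 2.4.2.2.4 are blacked out. What follows takes 83% as given and assumes that it refers to a fully treated POST window.

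**Dilution of the rate ratio.** Let w be the gap share, g the gap rate relative to PRE, and RR the true treated rate relative to PRE. The observed ratio is w × g + (1 − w) × RR. For illustration take RR = 0.60 (an assumption) and w = 0.0767:

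- g = 1 (gap at the PRE rate): 0.0767 + 0.9233 × 0.60 = 0.631. The effect looks smaller than it is.
- g = 0.5: 0.0384 + 0.5540 = 0.592. The effect looks slightly larger.
- g = 0 (no gap events): 0.554. The effect looks larger still.

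The sign changes at g = RR, where the gap rate equals the treated rate.

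**Power if g = 1, simple scaling.** The standardized effect that gives 83% power at one-sided 2.5% is z(0.83) + 1.96 = 0.954 + 1.960 = 2.914. A gap of d days in every subject shrinks the PRE–POST difference by the factor 1 − d/365.

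- 14 days: 2.914 × 0.9616 = 2.802; 2.802 − 1.960 = 0.842; power 80.0%.
- 28 days: 2.914 × 0.9233 = 2.691; 2.691 − 1.960 = 0.731; power 76.7%.

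**Power if g = 1, log rate ratio.** A second calculation used a Wald test with independent quasi-Poisson counts, n = 100, and SE = √{φ[1/(nλT_pre) + 1/(nλ·RR·T_post)]}. The PRE rate λ (0.5 to 1.5 per year) and the dispersion φ (1 to 2) are assumed ranges, not document figures. For each pair, the RR giving 83% power was solved for and then diluted.

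Worked case, λ = 1.0 and φ = 1: RR = 0.625 gives 83%. With 28 days at the PRE rate it becomes 0.0767 + 0.9233 × 0.625 = 0.654, and power is 76.2%.

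Across all the assumed values:

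| Gap | POST = 12 months from enrollment | POST to 12 months after procedure |
|---|---|---|
| 14 days | 79.7% to 79.9% | 80.8% to 81.1% |
| 28 days | 76.0% to 76.4% | 78.5% to 79.1% |

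The two methods agree to within about a percentage point for a POST window of 12 months from enrollment. Both treat every subject as having the full gap.

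**The case against.** Several points on the other side stand.

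**Redaction.** Text directly after the definition in SAP 2.3.2.2.4 is blacked out, as are Protocol 9.2.2.2.4, the Single-arm Attempted Procedure population and the power inputs. Exposure start or the handling of pre-procedure events could be set there. The visible text shows that POST is defined from enrollment. It does not show that the gap is unhandled, or that the 83% ignored it. If hidden text starts exposure at the procedure, it conflicts with the visible definition, which would still need correcting.

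**Direction.** A reader might infer that the enrollment anchor must bias the test against the device and cost power. The documents do not support that. Protocol 6.3.1 requires 30 days of stability on adequate treatment, and Protocol 9.1.2 limits the analysis to subjects who receive the device. Both could make the gap rate low, and a gap rate below the treated rate reverses the bias.

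**Size.** Twenty-eight days is the longest scheduled gap, not a typical one. Baseline may fall on the day of treatment (Protocol 7.3.1). If enrollment is read as the eligibility reconfirmation at baseline, the maximum is 14 days. Seven days gives about 81.5% by the simple scaling. In the other direction, postponement can exceed 28 days.

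**Postponement.** A reader might also infer that decompensating Single-arm subjects add their events to POST while they wait. In Protocol 7.6.2.4 the change-in-condition rule names only Device group and roll-in subjects, and its examples do not include HF decompensation. Only the postponement for echo findings is worded generally.

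**Merit of the current anchor.** Enrollment gives contiguous windows that lose no event. If gap events run at the PRE rate, it is conservative. Dropping the gap would then make the device look better, which is why gap events must stay visible.

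**Conclusion.** On the visible text, the Single-arm POST window starts before treatment by 0 to 28 scheduled days, or longer after an echo-related postponement. Pre-procedure HF hospitalizations are therefore counted as post-treatment. This does not match the procedure-based visit and MAE clocks.

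The effect is modest and its sign is not known. With gap events at the PRE rate, a full gap in every subject and a stated 83% that assumed fully treated time, power is about 80% to 81% at 14 days and about 76% to 79% at 28 days. The 28-day values fall below the 80% stated in SAP 2.4.2.2. With gap events rarer than treated events, the bias favors the device: with none in a 28-day gap, a true ratio of 0.60 is seen as about 0.55. It would go too far to conclude that the 83% is wrong, since its inputs are hidden.

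The stakes are low. This endpoint is last of five in the Single-arm testing order (SAP 2.11.2) and has no part in trial success (SAP 2.7). The point is a cheap improvement.

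**What to change.** - Define POST in SAP 2.3.2.2.4 as the 12 months from the index procedure (femoral vein puncture).
- Keep PRE as the 12 months before enrollment. Table 1 in Protocol 7.15 collects the prior-12-month hospitalizations at screening, and Protocol 6.2.1 allows screening assessments up to 90 days before Eligibility Committee review. The history therefore needs updating to the enrollment date.
- Count the time from enrollment to procedure in neither rate, and list the HF hospitalizations that fall in it.
- Report the enrollment-anchored comparison as a sensitivity analysis.
- State whether the 83% power assumed POST to start at the procedure.

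Cost: a short SAP wording change, an instruction to bring the hospitalization history up to enrollment, one listing and one extra analysis. No new visits are needed; the procedure date already drives the visit schedule, and hospitalizations are already recorded at baseline and procedure. The downside is that gap events leave the main comparison. The listing and the sensitivity analysis keep them in view.

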2.3.2.2.5 Freedom from All-Cause Mortality and Tricuspid Valve Surgery at 12 Months

The null and alternative hypotheses are stated as:

Statistical Analysis Plan

$H_0: P_{12M}(\text{Survival}) \leq 65\%$ vs.

$H_1: P_{12M}(\text{Survival}) > 65\%$

where $P_{12M}(\text{Survival})$ is the freedom from all-cause mortality and tricuspid valve surgery (survival rate) at 12 months.

[REDACTED]

The null hypothesis will be rejected at a one-sided 2.5% level of significance.

2.3.3 Imaging Sub-Study

The imaging endpoints will be compared descriptively among MRI, CT and TTE at baseline, 30-days and 12 months on the imaging population.

2.4 Sample Size Calculations

2.4.1 Randomized Cohort

2.4.1.1 Primary Endpoints

Detailed simulations were conducted in order to determine the appropriate sample size to adequately power the study. The following assumptions were made to evaluate the power to demonstrate the superiority of the Device group to the control group:

- [REDACTED]

Statistical Analysis Plan

[REDACTED]

[REDACTED]

[REDACTED]

[REDACTED]

[REDACTED]

[REDACTED]

[REDACTED]

[REDACTED]

[REDACTED]

[REDACTED]

[REDACTED]

[REDACTED]

[REDACTED]

A simulation with 10,000 iterations was performed to determine the sample size and power for the primary endpoint. A total sample size of 350 randomized subjects provides approximately 83% power at the two-sided 5% significance level for the primary endpoint.

The assumptions for each component of the primary endpoint in the sample size calculation are determined collectively based on published literature on the use of the MitraClip device for the treatment of TR and preliminary data derived from the TRILUMINATE. Since the TRILUMINATE study is still ongoing with limited data available, the information from the COAPT PMA submission is also used to leverage the assumptions.

[REDACTED]

[REDACTED]

[REDACTED]

[REDACTED]

[REDACTED]

[REDACTED]

[REDACTED]

[REDACTED]

[REDACTED]

[REDACTED]

[REDACTED]

[REDACTED]

[REDACTED]

[REDACTED]

[REDACTED]

[REDACTED]

[REDACTED]

[REDACTED]

Statistical Analysis Plan

[REDACTED]

- [REDACTED]
- [REDACTED]

[REDACTED]

2.4.1.2 Secondary Endpoints

2.4.1.2.1 TR Reduction to Moderate or Less at 30-Day Post Procedure

The power calculation for the TR reduction to moderate or less at 30-day post-procedure is based on the following assumptions:

- [REDACTED]
- [REDACTED]
- [REDACTED]

Ten thousand (10,000) simulations were performed. Based on the assumptions, with 350 randomized subjects, the power is approximately 93% to reject the null hypothesis at a two-sided 5% level of significance.

Statistical Analysis Plan

The assumption for the secondary endpoint of TR reduced to moderate or less at the 30-day visit is determined collectively based on the preliminary data derived from TRILUMINATE as well as the trending of reduction in Mitral regurgitation at 30-day visit in COAPT:

- █ [REDACTED]
- █ [REDACTED]
- █ [REDACTED]
- █ [REDACTED]

Therefore, for the TRILUMINATE PIVOTAL study, the rates of TR reduction to moderate or less at the 30-day visit were conservatively assumed to be 70% vs 50% for the Device vs Control groups respectively.

2.4.1.2.2 Freedom from Major Adverse Events (MAE) at 30-Day Post Procedure

The power calculation for the major adverse events at 30-day post procedure is based on the following assumptions:

- [REDACTED]
- █ [REDACTED]
- █ [REDACTED]
- █ [REDACTED]
- █ [REDACTED]
- █ [REDACTED]
- █ [REDACTED]
- █ [REDACTED]

Ten thousand (10,000) simulations were performed to calculate the sample size and power for this secondary endpoint. Based on the assumptions, with approximately 175 subjects randomized to the Device arm, the power is > 95% to reject the null hypothesis against the performance goal of 90% at a one-sided 2.5% level of significance.

The event rate of MAE is determined based on the preliminary result of MAE from TRILUMINATE study as of the data cut-off date (November 29, 2018). There were 1.2% (1/85) of subjects with an MAE for new onset renal failure at 30 days. The 95% one-sided upper confidence limit is 5.5%.

Statistical Analysis Plan

2.4.1.2.3 Change in Quality of Life (Kansas City Cardiomyopathy Questionnaire, KCCQ) at 12 Months over Baseline

The power calculation for the change in KCCQ overall summary score at 12 months over baseline is based on the following assumptions:

- █ [REDACTED]
- █ [REDACTED]
- █ [REDACTED]
- █ [REDACTED]
- █ [REDACTED]
- █ [REDACTED]
- █ [REDACTED]
- █ [REDACTED]

Ten thousand (10,000) simulations were performed to calculate the sample size and power for this secondary endpoint. Based on the assumptions, with 350 randomized subjects, the power is above 90% to reject the null hypothesis at a two-sided 5% level of significance.

2.4.1.2.4 Change in 6MWT (Six Minute Walk Test) Distance at 12 Months over Baseline

The power calculation for the change in 6MWT distance at 12 months over baseline is based on the following assumptions:

- █ [REDACTED]
- █ [REDACTED]
- █ [REDACTED]
- █ [REDACTED]
- █ [REDACTED]
- █ [REDACTED]
- █ [REDACTED]
- █ [REDACTED]

Ten thousand (10,000) simulations were performed to calculate the sample size and power for this secondary endpoint. Based on the assumptions, with 350 randomized subjects, the power is above 90% to reject the null hypothesis at a two-sided 5% level of significance.

Statistical Analysis Plan

The clinical assumptions for the changes in 6MWT distance are derived collectively from data from TRILUMINATE I as well as COAPT:

- █ [Redacted]
- █ [Redacted]
- █ [Redacted]
- █ [Redacted]
- █ [Redacted]
- █ [Redacted]
- █ [Redacted]
- █ [Redacted]
- █ [Redacted]

